11 REGISTRATION, DATA COLLECTION AND MANAGEMENT

11.1 Registration of participants

Practice registration: takes place during the initiation visit by a trained study team member. The participating practices give written informed consents of a general practitioner (GP) and a healthcare assistant (HCA) to participate in the study and to implement the study protocol (centre registration form).

Patient registration: at the IGP the incoming telefaxes of registration forms and signed informed consents are controlled (patient ID is consistent with the patient ID of the random list, signature of the patient, fulfilment of in- and exclusion criteria) and patient registration is confirmed to the practice by telefax.

11.2 Data collection

11.2.1 Data collection of participating HCA and GP

First documentation takes place at the initiating visit at the trial site: social demography of HCA and GP and practice characteristics as well are documented in paper based forms (each one per HCA and GP and practice).

11.2.2 Data collection of participating patients

Examinations and documentation of the patient related data take place regularly during the aforementioned visits 1-3. Visits 1-3 take place in months 0, 6 and 9 (+/- one month) following the inclusion of the patient in the trial. An overview of the individual examinations is given in table 1 (see pp 23). The content of the individual examinations to be documented is described in detail in section 11.3 (see below). At each visit the following documents are collected:

- The patient registration document (T0) and control sheets (T1, T2) filled in by HCA and GP are sent to the IGP via telefax at the day of the patient's visit to the practice.
- The paper based case report form (CRF) completed by the HCA and GP. Every CRF includes information on filling in the form. Necessary correction to the CRF must take place in the following manner: invalid data should be crossed out whereby crossed-out details should be authorised with the date and the investigator's initials.
- The completed patient questionnaire (paper based as well): The patient questionnaires, including an envelope, will be issued by the HCA. The patients fill in the questionnaires in the practice and put them in the envelopes which they then seal themselves (confidentiality of information with respect to trial site). If necessary, the HCA provides help filling in the patient questionnaires and keeps an eye on the return of the completed documents.

The completed CRFs and the sealed envelope with the completed patient questionnaire will be put in the return envelopes (no stamp required) at the trial site and promptly returned to the IGP by mail.

Within five working days as after arrival of the patient registration document / control sheets, trial employees will contact the patient to conduct the telephone interview. Information from these interviews will be entered directly into the entry mask of an SQL data bank (Access®). If the interviewer cannot reach the patient, further attempts to do so will be made on the following days. After the fifth unsuccessful attempt, the responsible practice will be contacted by the trial assistant and asked for information on the whereabouts of the patient. If the attempts to contact the patient fail within one month, the telephone interview for this visit is considered as missing.

11.2.3 Data collection of non-participating patients

If a patient from the random list (see 5.3.2) does not agree to participate, or is not included for any other reason (e.g. the recruitment goal per practice is already fulfilled), then the following data will be documented on the patient registration form pseudonymously – age, gender, in- and exclusion criteria (without MMSE score), reason for non-inclusion. The documentation of further data and especially personal data such as name, date of birth or telephone

number is not permitted. The patient registration forms for those patients who are not included will also be faxed to the IGP and the originals will remain on the files of the GP and checked by the monitor after completion of the trial.

11.3 Description of data sets

11.3.1 Data set to determine practice profile

- Single-handed practice / group practice (incl. ambulatory healthcare centre, with the number of physicians and the question for additional general practitioners),
- Location: Big town (> 100.000 inhabitants) / middle size town (20.000 to 100.000) / small town (5.000 to 20.000) / rural area (< 5.000 inhabitants)
- Clinical specialisation of practice
- Number of registered patients in most recent quarter [in categories: 0 – 499, 500 – 999, 1000 – 1499, 1500 – 1999, 2000 and over]
- Quality management system used in practice
- (Brand name of practice EDV to provide any necessary support for the study by the IGP)

11.3.2 Data set to determine profile and sociodemographics of the GP

- Practice-ID as provided by the IGP, GP-ID (consecutively for each participating GP)
- Age, gender of GP
- GPs professional practice experience (year doctor commenced private practice)
- Years of clinical experience in total
- GP: Specialist in primary care, specialist in internal medicine, GP / doctor with no specialist area
- Previous participation in a former clinical trial and name of trial

11.3.3 Data collection to determine profile and sociodemographics of the HCA

- Practice-ID as provided by the IGP, HCA-ID (consecutively for each participating HCA)
- Age, gender of HCA
- School leaving certificate, professional and additional qualifications
- Years of professional experience as health care assistant and at trial site
- Type of employment
- Previous participation in a former clinical trial and name of trial

11.3.4 Patient registration form

Registration form for every patient on random list with

- Practice-ID as provided by the IGP, GP-ID, patient-ID as used in practice computer, month and year of birth, age, gender
- Checklist for in- and exclusion criteria (items to be marked with a cross, exclusive MMSE score)
- Decision not to participate (if possible with reasons)
vs. patient not approached (as recruitment target already reached)
vs. readiness to participate (patient's written informed consent is on hand)
- If written informed consent on hand:

- Name, first name, patient's phone number
- MMSE Score

11.3.5 Case report forms (see prototype in appendix)

Sociodemographics and basic clinical data: insurance status (private, statutory or differing), name of insurance company, participation in one of the disease management programs (diabetes mellitus I/II, coronary artery disease, breast cancer, COPD, asthma), home care situation and assessment of quality of care, height (measured), weight (measured), current diagnoses, allergies / intolerances, consultations with specialists (specialisation of physician) and hospital stays during the last six months (date of admission to / release from hospital; inpatient, day hospital care, outpatient, inpatient rehabilitation; reason for treatment).

Laboratory: Laboratory values for serum electrolytes (sodium and potassium) and serum creatinine that are already available in the practice. The most recent values should be taken along with the date of the test, but should not be more than 12 months prior to patient inclusion in the trial.

Current medication: trade name, strength, application, dosage, indication, duration of therapy at time of documentation (more or less than three weeks) and estimated importance of the particular medicine within the concept of the therapy as a whole (4-point Likert scale: very important – important – of little importance – not important).

Current diagnoses: all active diseases of the patient at the time of documentation (acute and chronic diseases) and treatable conditions (e.g. hypertension without end organ failure, positive medical history for gastric ulcer)

Modified Cumulative Illness Rating Scale (CIRS): Assessment of organs / organ systems / areas (15 items in total) according to severity of impairment (5-point Likert scale: no impairment to extreme impairment),⁵⁵⁻⁵⁷ with one supplementary item "chronic pain syndrome" and one supplementary response category entitled "not applicable" if the named organ (system) is not affected.

Expanded Charlson Comorbidity Index: List of underlying diseases in the Charlson Comorbidity Index⁵⁸ plus relevant diseases and situations that often result in contraindications to specific medication.

11.3.6 Patient questionnaires (see prototype in appendix)

Sociodemographics: marital status, number of persons living in the household (i.e. household composition), home care, socioeconomic status (best school leaving certificate, professional training), housing indicators (population size: big town [>100.000 inhabitants] / middle size town [20.000 to 100.000] / small town [5.000 to 20.000] / rural area [<5.000]; housing tenure [home ownership]; place attachment [home / neighbourhood]).

Generic health related **quality of life** (EuroQoL, EQ-5D),^{39,40} maintenance of **functional status** (Vulnerable Elderly Survey, VES-13),⁴³ **Beliefs about Medicines Questionnaire** (BMQ),²⁷ **severity of chronic pain** (in accordance with M. v. Korff, J. Ormel et al.),⁵¹ satisfaction with shared decision making (Man-Son-Hing scale),²⁹ future life expectancy (future expectation / expected lifetime duration / desired lifetime duration).^{48,49}

11.3.7 Telephone interview with patients

At each visit a trained employee from IGP conducts interviews with patients using an interview guide (see appendix) and enters the answers directly into an Access-data base.

Medication incl. OTC drugs and supplements (trade name, National Drug Code, dose, prescribed by whom, duration of intake more or less than three weeks) currently being taken on a regularly basis; medication to be taken as needed, including OTC drugs (in case of what symptoms, single dose, total maximum dose); autonomous preparation and intake of medication vs. support from third parties, known allergies, symptoms for potentially adverse drug reactions.

Consultation of other healthcare providers: Other healthcare providers consulted during the last six months (name, location, profession/specialisation, number of consultations, reason(s) for consultation, and referral by GP vs. direct access).

Sherbrooke Questionnaire: Five items to identify positive predictors (lives alone, uses a walker, self-reported visual, hearing and memory impairment, sixth item already one of inclusion criteria: more than three long-term medicines daily).⁵⁹

Use of medical aids and special therapeutic measures: Use of visual and/or hearing aids, use of home oxygen therapy, participation in dialysis therapy, ask about implant devices (pacemaker, defibrillator)

Patient interview on depression (Geriatric depression scale, GDS)^{60,61}

Patient interview on adherence (Self reported adherence according to Morisky)⁴⁷

Verbal fluency test: Patients are asked to tell as many animals as possible within one minute.⁶² Answers are audiotaped and time is controlled by a stop watch. After the interview is finished, the interviewer transcribes the audiotape into the database and deletes the tape soon after.

11.3.8 Documentation of intervention

After completion of the trial the data from the completed intervention tools (MediMoL, AiD+) will be analysed (intervention group only).

11.4 Data management

The responsible trial employee will check all incoming post is complete and confirm receipt by marking it (date of receipt, date of check, initials - tracking). The due dates for sending the documentation is described in a guideline on data flow in the investigator's file. Missing information will be collected in preparation for the following query management (see below).

After confirmed reception of data it will be entered into an SQL trial database (Access©) by one of the trial employees. A data check will take place of this database according to pre-defined trial rules (range-, validity, and consistency checks according to defined SOPs developed during the course of the trial and documented in the TMF). Queries for the investigators that may crop up as a result of this data check will be formulated by the IGP (see below, Query management). Sending, collecting and processing patient data will always take place under the patient identification number (Pat.-ID) pseudonym.

Coding will be used for some of the data, partly when the data is entered. In retroactive processing steps, some free text information will be encoded into new variables. The encryption specifications will be deposited in the TMF.

11.5 Data Validation (Query management)

Data recognized as missing during the confirmation of receipt check will be collected for each practice using the patient IDs and then faxed to the trial sites as a written request for completion. These fax requests will be filled in and signed by the investigator and then faxed back to the IGP. The receipt of the returned faxes will then be confirmed and the process continued until all missing data have been collected. The checked data will then be forwarded and entered into the database, as described above.

Follow-up enquiries resulting from the data plausibility check will also be collected for each practice and formulated as a written fax request using the patient identification number. They will then be dealt with in the same way as described under (missing data).

If possible, query management will be undertaken during regular practice visits in order to limit the number of fax requests. However, timely query management has first priority.

All CRFs, patient questionnaires, queries and answers will be kept at the IGP in paper-form. Changes to the Access database will be documented in an audit trail. The necessary programming instructions will be developed along with the data management concept.

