4 STUDY DESIGN

PRIMUM is scheduled as a pragmatic, cluster-randomised controlled trial with the general practice as the unit of randomisation. A clustered design (practices as clusters) was chosen to reduce treatment group contamination, since HCA and GP trained in the intervention will plausible not be able to provide usual care.

Allocation concealment will be disclosed after completion of the baseline documentation for all study patients within a practice but before the intervention begins. Intervention will take place on practice level.

Due to the type of intervention, neither GPs and their patients nor the PRIMUM study team will be blinded to the treatment allocation. However, allocation will neither be revealed to the pharmacologist who is responsible for the MAI rating nor to the study statistician who is responsible for the statistical analyses.

To reduce the contamination of the control group only general information of the treatment in the intervention group is provided in the regular study protocol (a complex intervention including a checklist based pre-consultation interview by the HCA and the use of an internet based CDSS). Detailed information about the intervention treatment is provided only to the intervention group as an appendix to the study protocol in the intervention training.

All primary and secondary outcomes will be measured at patient level at baseline (T0), and at follow-up: 6 months after baseline (T1) and 9 months after baseline (T2).

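### As written, the query rule sends gaps and implausible values in the sealed patient questionnaires to the unblinded practice, with no exemption for patient-reported items

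*Protocol*

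**What the plan says.** Section 11.2.2 separates the questionnaire from the practice. Patients complete it on site and "put them in the envelopes which they then seal themselves (confidentiality of information with respect to trial site". It then travels with the practice's own form: "The completed CRFs and the sealed envelope with the completed patient questionnaire will be put in the return envelopes".

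Section 11.4 describes what happens on arrival: "The responsible trial employee will check all incoming post is complete and confirm receipt by marking it". It adds: "Missing information will be collected in preparation for the following query management". No type of document is left out.

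Section 11.5 sends the missing data found at receipt to the practice by fax. "These fax requests will be filled in and signed by the investigator and then faxed back to the IGP". Receipt of the answers is "confirmed and the process continued until all missing data have been collected". Queries from the plausibility check take the same route.

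On blinding, section 4 states that "neither GPs and their patients nor the PRIMUM study team will be blinded to the treatment allocation". Sections 4 and 6 have the practice learn its allocation once baseline documentation for its patients is complete.

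**The concern.** The questionnaire carries outcomes that only the patient can report: quality of life, function, beliefs about medicines, pain, satisfaction with shared decisions, and expected and desired lifetime. If a blank or odd answer at follow-up goes to the practice, the value that comes back is late and is supplied by, or passes through, a doctor who knows the arm. In intervention practices that doctor also held the medication consultation. The Man-Son-Hing scale is the most sensitive case, because it asks the patient to rate decision making shared with that doctor.

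Pain matters for another reason. Section 8.1.3 includes it partly to show whether the intervention worsens pain management, and section 10 plans no safety monitoring or adverse event reporting. Any distortion that differs between arms would enter the comparison as if it were patient data.

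**Working it through.** The protocol states no figure on this point, so the check follows the documents through the process.

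1. **What arrives.** Under 11.2.2 the CRF and the sealed questionnaire share one return envelope, so the questionnaire is incoming post.
2. **What is checked.** Section 11.4 applies the completeness check to all incoming post, and what is missing goes on to query management. The later range, validity and consistency checks run on the trial database, again without separating patient-reported fields.
3. **Where the query goes.** Section 11.5 collects gaps by practice and faxes them to the site. There is no route back to the patient.
4. **Who answers.** The investigator does. Section 5.2.1 shows that this is the practice physician.
5. **When it stops.** It stops when no gap remains. No provision lets a questionnaire item stay blank.
6. **What the answerer knows.** At T1 and T2 the practice knows its arm (sections 4 and 6). T0 queries may be answered before disclosure, so the unblinded route concerns follow-up.
7. **Conflict with 11.2.2.** The seal keeps answers from the site. A query about a blank returns the item to the site for completion. A plausibility query may also reveal the answer given.

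**Which outcomes are exposed.** Section 11.3.6 puts EQ-5D, VES-13, BMQ, chronic pain, the Man-Son-Hing scale and the life-expectancy items in the questionnaire. The MAI is not there; under sections 4 and 8.1.1 it is rated by a pharmacologist blinded to allocation. Depression, self-reported adherence and verbal fluency come from the telephone interview and are entered directly, so the post check does not reach them. The plausibility route does not exempt them either.

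**Size.** In general terms, bias in a score = (share of follow-up scores affected) × (difference between arms in the shift, in SD). The protocol gives neither input. With assumed shares of 5% to 30% and assumed shifts of 0.2 to 1.0 SD:

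- lowest: 0.05 × 0.2 = 0.01 SD
- highest: 0.30 × 1.0 = 0.30 SD

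The ends differ by a factor of 30, and both come from assumption alone. The formula also shifts whole scores. One filled item in a multi-item instrument would move the score by less.

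**The case against.** Section 11.5 never names questionnaire items as query items. A narrower reading is possible: 11.4 speaks of queries for investigators, and the rule in 11.2.2 for corrections initialled by the investigator is attached to the CRF, so investigators may be meant to answer only for what they documented. The wording of 11.7, which brackets the questionnaires with the CRF, points the other way. That bracket also takes in the final report, so it settles little. The narrower reading may be what was intended, but no sentence says so, and the scope of the receipt check contradicts it.

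Three stronger conclusions are tempting, and the protocol does not support them.

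- **That the GP answers in the patient's place.** Section 11.5 says who completes and signs the fax, not whether the patient is asked first. The rule permits a proxy answer and does not prescribe one.
- **That such items could not be separated afterwards.** Section 11.5 retains questionnaires, queries and answers on paper, so the origin of an item can be traced by hand. The audit trail covers database changes and may miss gaps filled before entry. The protocol plans no flag variable.
- **That a given bias or inflated error rate follows, or that harm through pain would be hidden.** The inputs are assumed. The ICC of 0.03 and d = 0.3 in section 12.3 are MAI planning values, not values for these outcomes.

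It is also fair that a query about a blank discloses no answer, and that 11.2.2 lets the healthcare assistant help with completion, so separation from the site was never absolute. Help at the visit with the patient present still differs from later completion by fax. Finally, the SOPs, the data management concept and the data management and validation plan are not shown and might narrow the rule. The protocol's own text should not say the opposite.

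**Conclusion.** The point holds as a conflict in the protocol's text. Sections 11.4 and 11.5, taken literally, route blank and implausible questionnaire items at T1 and T2 through an unblinded GP, while 11.2.2 seals those answers from the practice. This can bias the questionnaire outcomes.

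Severity is low to moderate. The primary MAI endpoint does not use the questionnaire, and section 12.2 treats only the primary analysis as confirmatory. The magnitude is unknown; the range of 0.01 to 0.30 SD shows only how far assumptions can move it. The conclusion rests on two readings: that incoming post includes the questionnaires, which 11.2.2 supports directly, and that no exemption exists, which is true of the protocol but cannot be checked in the plans not shown.

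**What to change.** In 11.4 and 11.5:

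- Limit investigator-completed missing-data and plausibility queries to practice-documented data, meaning the registration form and the practice part of the CRF.
- State that patient-questionnaire items are not sent to, shown to or completed by the practice.
- State that a plausibility check does not overwrite a patient's own answer.
- Leave unanswered items missing, and handle them by the instrument's scoring rule and then by the missing-data analysis under 12.2.

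Repeat the limit in the data management and validation plan. If queries of this kind have already been answered, identify those items from the retained paper and flag them in the database.

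The cost is a sentence or two in the protocol, slightly more missing questionnaire items, and fewer queries for practices. No visit, instrument or sample size changes.

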11.6 Quality control and quality assurance

The study team of the IGP guarantees that all processes in the trial will comply with the Good Clinical Practice (GCP) guidelines, the legal requirements and the SOPs of the IGP. General practitioners and healthcare assistants of the trial sites will be educated on the trial requirements during the investigators' training at the initiating practice visit.

Monitoring: The IGP will be responsible for monitoring the trial. A study employee will regularly visit the trial sites (at least two visits per practice) to ensure that

- the rights of the trial participants are protected,
- the study data are documented completely and in a correct manner and can be verified for defined variables in the source data (selection of appropriate variables will be defined in the data management and validation plan of the trial)
- the trial is conducted in accordance with the study protocol (and its amendments where required) and complies with GCP and legal requirements at the trial site.

Scientific Advisory Board: The board gives scientific advice in questions on planning, conducting and analysing the trial.

